## **Response Criteria**

### **Evaluation of Target Lesions**

- **Complete Response (CR)** - Disappearance of all target lesions.
- **Partial Response (PR)** - At least a 30% decrease in the sum of the LD of target lesions, taking as reference the baseline sum LD.
- **Progressive Disease (PD)** - At least a 20% increase in the sum of the LD of target lesions, taking as reference the smallest sum LD recorded since the treatment started or the appearance of one or more new lesions.
- **Stable Disease (SD)** - Neither sufficient shrinkage to qualify for PR nor sufficient increase to qualify for PD, taking as reference the smallest sum LD since the treatment started.

### **Evaluation of Non-Target Lesions**

- **Complete Response (CR)** - Disappearance of all non-target lesions and normalization of tumor marker level.
- **Incomplete Response/Stable Disease (SD)** - Persistence of one or more non-target lesion(s) or/and maintenance of tumor marker level above the normal limits.
- **Progressive Disease (PD)** - Appearance of one or more new lesions and/or unequivocal progression of existing non-target lesions. Unequivocal progression of an existing lesion can only be categorized as such if actual measurement with a ruler or caliper is not required and progression is obvious on visual inspection. For malignant ascites, PD is defined as an increase in abdominal girth (abdominal circumference measured at a fixed point at the level of the iliac crest) greater than 25% over baseline, with a worsening of clinical signs and symptoms. Malignant pleural or pericardial effusions will be considered PD only if there is worsening of associated symptoms.

## Evaluation of Overall Response

Table 3.7.5-1 provides overall responses for all possible combinations of tumor responses in target and non-target lesions with or without the appearance of new lesions.

**Table 3.7.5-1 Evaluation of Overall Response**

Target Lesions (T)	Non-target Lesions (NT)	New Lesions	Overall Response
CR	CR	No	CR
CR	No-NT a	No	CR
No-T b	CR	No	CR
CR	Non-PD and not Unknown	No	PR
PR	Non-PD and not Unknown	No	PR
PR	No-NT	No	PR
SD	No-NT	No	SD
SD	Non-PD and not Unknown	No	SD
No-T	Non-PD and not Unknown	No	SD
PD	Any	Yes/No	PD
Any	PD	Yes/No	PD
Any	Any	Yes	PD
Unknown	Non-PD	No	UNK
Non-PD	Unknown	No	UNK

a No-NT is defined as no non-target lesions at baseline.

b No-T is defined as no target lesions at baseline.

## Karnofsky Performance Status

Karnofsky performance status (see [Appendix 1](#)) will be performed as described in [Table 3.6-1](#), [Table 3.6-2](#), and [Table 3.6-3](#).

### **3.7.6 Pharmacodynamic Evaluations**

#### **3.7.6.1 Biomarker Analysis**

Blood collection for assessment of selected soluble proteins and tumor biomarkers and other biological processes will be performed as described in [Table 3.6-1](#), [Table 3.6-2](#), and [Table 3.6-3](#). Biomarkers to be evaluated include specific circulating soluble proteins, ie, PDGF-AA, PDGF-AB/BB, bFGF, VEGF, soluble Flt-1, and/or PlGF, as well as tumor markers when appropriate such as PSA and CA-125. Circulating tumor cells will also be assessed for genetic variations, PDGFR $\alpha$ , and expression levels of related signaling proteins when circulating tumor cells are available. Additionally, evaluation of the effects of genetic variation and PDGFR $\alpha$  expression levels will be performed when fresh and/or archival tumor samples are available. Specific biomarkers may be used to assign subjects to the expansion phase if target saturation and biological efficacy is observed below the MTD or maximum dose (15 mg/kg).

Details regarding blood sample collection for assessment of biomarkers are described in the Specimen Collection Manual provided by the sponsor.

#### **3.7.6.2 RNA Analysis**

Whole blood samples will be used to analyze the effects of MEDI-575 on levels of messenger RNA (mRNA) sequences. This analysis is performed using Affymetrix® whole genome expression array and taqMan-based assay on selected panel of genes.

#### **3.7.6.3 DNA Analysis (Optional)**

To investigate characteristics associated with subject's clinical response and safety, one blood sample (8.5 mL) will be collected at screening and frozen at  $-80^{\circ}\text{C}$  for DNA sample preparation. The sample will be frozen and stored for use in exploratory analyses.

The collection of blood for DNA analysis is optional in this study. The completion of a separate informed consent form (Informed Consent Form for DNA Analysis) is requested but not required for participation in the study. Subjects who do not wish to have the DNA test done will still be eligible for the study. Subjects who elect to have the DNA test done may, at any time, request that the blood collected for DNA analysis be destroyed.

All specimen and subject identifiers will be removed from the DNA blood samples such that under no circumstances can the DNA blood samples be linked back to a specific subject. In most cases, this will require that DNA blood samples have current labeling removed and the tubes relabeled. Special labeling capable of adhering to frozen tubes must be used. If it is not possible to remove the original labeling, then it must be determined whether the DNA blood samples can go through a freeze-thaw cycle and be re-aliquoted to maintain confidentiality. All relabeled DNA blood samples must be cross referenced to the original demographics in a secure database to ensure that only appropriate laboratory personnel have access to these data. These data will be utilized in the event that at any time a subject requests that a sample be destroyed. A special release must be obtained prior to use of specified DNA blood samples.

### **3.8 Subject Completion of Study and Loss to Follow-up**

Subjects will be considered to have completed the study if they were followed until the end of the study (defined as 1 year after the last subject entered the study). It should be specified on the source document whether or not the subject completed the study follow-up procedures through the end of study.

Subjects will be considered lost to follow-up only if no contact has been established by the time the study is completed such that there is insufficient information to determine the subject's status. Investigators should document attempts to re-establish contact with missing subjects throughout the study period. If contact with a missing subject is re-established, follow-up should resume according to the protocol.

## **4 Safety Assessment**

### **4.1 Adverse Events**

#### **4.1.1 Definition of Adverse Events**

As defined by the ICH Guideline for Good Clinical Practice (CPMP/ICH/135/95), an AE is:

- Any untoward medical occurrence in a subject or clinical investigations subject administered a pharmaceutical product and which does not necessarily have to have a causal relationship with this treatment.

- An AE can therefore be any unfavorable and unintended sign (including an abnormal laboratory finding), symptom, or disease temporally associated with the use of a medicinal product, whether or not considered related to the medicinal product.

An AE includes but is not limited to:

- Any clinically significant worsening of a pre-existing condition;
- An AE occurring from overdose (ie, a dosage higher than that prescribed by a healthcare professional for clinical reasons, or a dosage higher than that described on the marketed product label) of an investigational or marketed product, whether accidental or intentional;
- An AE occurring from abuse (eg, use for nonclinical reasons) of an investigational or marketed product;
- Any laboratory abnormality that is judged by the investigator to be medically significant (except as noted in Section 4.10);
- An event related to a medical procedure or associated with the discontinuation of the previous use of an investigational or marketed product required by protocol (protocol-related AE).

#### **4.1.2 Study Reporting Period for Adverse Events**

All AEs that are not classified as serious (for which an expanded reporting period is used, see Section 4.2 below) and occur after a subject has received the investigational product through 30 days after the last dose of MEDI-575 must be reported by the investigator.

Any new sign or symptom, disease, or other untoward medical event that occurs after the subject/legal representative signs the informed consent form but before the subject has received investigational product, and which may possibly be causally related to the protocol (ie, results from a required procedure or from withdrawal of prior medication), must be reported by the investigator as an adverse event in the same way as adverse events that occur after the subject receives investigational product.

#### **4.1.3 Recording of Adverse Events**

Adverse events will be reported using a recognized medical term or diagnosis that accurately reflects the event. Adverse events will be assessed by the investigator for severity, relationship to the investigational product, possible etiologies and whether the event meets criteria as a SAE and, therefore, requires immediate notification of the sponsor. See Section 4.2.1 for the definition of SAEs, and Section 4.3 and Section 4.4 for guidelines for

assessment of severity and relationship, respectively. If the event has not resolved at the end of the study reporting period it will be documented as ongoing. If an AE evolves into a condition that becomes “serious” it will be reported on the SERIOUS ADVERSE EVENT (SAE) REPORT FORM.

## **4.2 Serious Adverse Events**

### **4.2.1 Definition of Serious Adverse Events**

An SAE is any AE that:

- Results in death;
- Is immediately life-threatening.

This term refers to an event in which the subject was at risk of death at the time of the event; it does not refer to an event that hypothetically might have caused death if it were more severe.

- Requires inpatient hospitalization or prolongation of existing hospitalization.

In general, hospitalization signifies that the subject has been detained (usually involving at least an overnight stay) at the hospital or emergency ward for observation and/or treatment that would not have been appropriate in an outpatient setting. Complications that occur during hospitalization are AEs. If a complication prolongs hospitalization or fulfills any other serious criteria, the event is serious. When in doubt as to whether “hospitalization” occurred or was necessary, the AE should be considered serious. Hospitalization for elective treatment of a pre-existing condition that did not worsen from baseline is not considered an AE.

- Results in persistent or significant disability/incapacity.

The term disability means a substantial disruption of a person’s ability to conduct normal life functions. This definition is not intended to include experiences of relatively minor medical significance such as uncomplicated headache, nausea, vomiting, diarrhea, influenza, and accidental trauma (eg, sprained ankle) which may interfere or prevent everyday life functions but do not constitute a substantial disruption.

- Is a congenital anomaly/birth defect in offspring of the subject.

A pregnancy should be reported to MedImmune Patient Safety as an immediately reportable event (IRE). A pregnancy should be followed for outcome and the health status of the mother

and the child. If the child is born with any congenital anomaly or birth defect, this should be reported to Patient Safety as a SAE.

- Is an important medical event that may jeopardize the subject or may require medical intervention to prevent one of the outcomes listed above.

Medical or scientific judgment should be exercised in deciding whether expedited reporting is appropriate in this situation. Examples of medically important events are intensive treatment in an emergency room or at home for allergic bronchospasm, blood dyscrasias, or convulsions that do not result in hospitalizations; or development of drug dependency or drug abuse.

A serious event related to a medical procedure required by protocol prior to dosing of the investigational product should also be reported to Patient Safety as an SAE (protocol-related SAE).

#### **4.2.2 Study Reporting Period for Serious Adverse Events**

The reporting period for SAEs is the period immediately following the time that written informed consent is obtained through 30 days after the last dose of MEDI-575. After the initial SAE report, the investigator is required to follow each subject proactively and provide further information on the subject's condition to MedImmune Patient Safety.

All SAEs should be followed up to resolution by the investigator, even if this extends beyond the study reporting period. Resolution of an SAE is defined as the return to baseline status or stabilization of the condition with the expectation that it will remain chronic.

At any time after completion of the study, if an investigator or qualified designee becomes aware of an SAE that is suspected by the investigator or qualified designee to be related to the investigational product, the event should be reported to MedImmune Patient Safety.

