#### **4.2.3 Notification of Sponsor of Serious Adverse Events**

**Within 24 hours of identifying an SAE, regardless of the presumed relationship to the investigational product, the investigator or qualified designee must complete the SAE Report form and fax to MedImmune Patient Safety.**

MedImmune contact information:

Patient Safety

MedImmune

MedImmune, as sponsor of the study being conducted under an Investigational New Drug Application (IND), is responsible for reporting certain SAEs as IND safety reports to the US Food and Drug Administration (FDA), other applicable regulatory authorities, and participating investigators, in accordance with the USA Code of Federal Regulations (21 CFR Parts 312.32 and 312.33) ICH Guidelines, and/or local regulatory requirements. MedImmune may be required to report certain SAEs to regulatory authorities within 7 calendar days of being notified about the event; therefore, it is important that investigators submit additional information requested by MedImmune as soon as it becomes available.

Investigators should provide all available information at the time of form completion. Investigators should not wait to collect additional information to fully document the event before notifying MedImmune of an SAE. When additional information becomes available, submit a follow-up SAE report form with the new information. Any follow-up information to an SAE also needs to be provided to MedImmune Patient Safety within 24 hours of learning of the new information.

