#### **4.2.4 Notification of Institutional Review Board or Independent Ethics Committee of Serious Adverse Events**

The investigator must comply with the applicable regulatory requirements related to the reporting of SAEs to the IRB or IEC. The IRB or IEC must be informed in a timely manner by the principal investigator of serious AEs occurring at their site during the study. Investigators must also submit safety information provided by MedImmune to the IRB or IEC as detailed in Section [7.2](#).

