## **7 Human Subjects**

### **7.1 Ethics and Regulatory Considerations**

The study will be conducted according to the Declaration of Helsinki, the International Conference on Harmonisation (ICH) guidelines on Good Clinical Practice (GCP), Protection of Human Subjects (21 CFR Part 50), Institutional Review Boards (21 CFR Part 56), and Investigational New Drug Application (21 CFR Part 312).

The protocol will be reviewed and approved by the Institutional Review Board (IRB) or Independent Ethics Committee (IEC) of each participating center prior to study initiation. Serious adverse events regardless of causality will be reported to the sponsor and to the IRB/IEC, and the investigator will keep the IRB/IEC informed as to the progress of the study.

The investigator will explain the nature of the study and will inform the subject/legal representative that participation is voluntary and that they can withdraw/can withdraw their child at any time. Written informed consent will be obtained from each subject/legal representative prior to the screening procedures required for entry into the study. A copy of the signed consent form will be given to every subject/legal representative and the original will be maintained with the subject's records.

To maintain confidentiality, all laboratory specimens, evaluation forms, reports and other records will be identified by a coded number and initials only. All study records will be kept in a locked file cabinet and code sheets linking a subject's name to a subject identification number (SID) will be stored separately in another locked file cabinet. Study records may be maintained electronically and require the same security and confidentiality as paper. Clinical information will not be released without written permission of the subject/legal representative, except as necessary for monitoring by regulatory authorities or the sponsor of the clinical study. The principal investigator must also comply with all applicable privacy regulations (eg, HIPAA 1996, EU Data Protection Directive 95/46/EC).

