## **7.2 Institutional Review Board (IRB) or Independent Ethics Committee (IEC)**

A list of IRB/IEC members should be obtained by the investigator and provided to the sponsor.

Any documents that the IRB/IEC may need to fulfill its responsibilities, such as protocol amendments, and information concerning subject recruitment, payment or compensation procedures, or information from the sponsor will be submitted to the IRB/IEC. The IRB/IEC's written unconditional approval of the study protocol, the informed consent form, and any other written materials to be provided to subjects will be in the possession of the investigator and the sponsor before the study is initiated. The IRB/IEC's unconditional approval statement will be transmitted by the investigator to the sponsor prior to shipment of investigational product supplies to the site. This approval must refer to the study by exact protocol title and number, and should identify the documents reviewed and the date of review.

Protocol modifications or changes may not be initiated without prior written IRB/IEC approval except when necessary to eliminate immediate hazards to the subjects or when the change(s) involves only logistical or administrative aspects of the study. Such modifications will be submitted to the IRB/IEC and written verification that the modification was submitted should be obtained.

The IRB/IEC must be informed by the investigator of informed consent form changes or revisions of other documents originally submitted for review; serious and/or unexpected adverse experiences occurring during the study; new information that may affect adversely the safety of the subjects or the conduct of the study; an annual update and/or request for re-approval; and when the study has been completed.

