## **8 Study Completion**

Study completion is defined as the date of the last assessment for the last subject in the study.

All materials or supplies provided by the sponsor will be returned to the sponsor upon study completion. The investigator will notify the IRB/IEC when the study has been completed.

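### Protocol Section 4.2.2 leaves suspected-related SAEs between 30 days after the last dose and study completion without a clear reporting rule, and no scheduled contact asks about them

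*Protocol*

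**What the plan says.** Section 4.2.2 of the protocol sets the period: "The reporting period for SAEs is the period immediately following the time that written informed consent is obtained through 30 days after the last dose". SAEs already reported are followed to resolution, even past that limit. For new events after the limit there is one further sentence, which covers only events suspected to be related to the product: "At any time after completion of the study, if an investigator or qualified designee becomes aware of an SAE that is suspected".

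Completion is a study-level date. Section 8 reads "Study completion is defined as the date of the last assessment for the last subject in the study". Section 3.8 counts subjects as completers if they were followed "until the end of the study (defined as 1 year after the last subject entered the study".

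Other sections bear on the same interval:

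- Section 4.2.3 requires notice to the sponsor "Within 24 hours of identifying an SAE, regardless of the presumed relationship to the investigational product", with no end date.
- Section 4.2.4 requires the IRB or IEC to be told of "serious AEs occurring at their site during the study".
- Section 7.1 states "Serious adverse events regardless of causality will be reported to the sponsor and to the IRB/IEC", again with no end date.
- Section 7.2 lists "serious and/or unexpected adverse experiences occurring during the study" among the matters the IRB or IEC must hear of.
- Section 4.7, on subjects taken off drug permanently, equates the full study period with the 30 days after the last dose.

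Table 3.6-3 marks AE/SAE assessment at the 30-day visit and not under the 3-monthly column. In Section 3.6, item 3 of the 3-monthly list, which applies to all subjects, covers survival status and later anticancer therapy.

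**The concern.** Taken with Section 8, Section 4.2.2 expressly requests a suspected-related SAE that surfaces after the whole study has closed. It does not request the same event during follow-up, when the information could still protect subjects receiving drug.

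Safety is the first primary objective of this first-in-human trial. Section 1.4 says enrollment has already reached Cohort 5, and Cohorts 6 and 7 and the expansion phase follow. Early subjects can therefore be past Day 30 while later ones are being dosed.

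A late related event matters to the cumulative review by the Safety Monitoring Committee (Section 4.6) and to Section 4.8 item 1. That item halts dosing and entry on a death at least possibly related to MEDI-575, in any subject and with no time limit. The rule works only if someone assesses the cause of each death, and the 3-monthly contact records that a subject died without asking why.

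**Working it through.** The protocol states no figure on this point, so there is none to reproduce. The check compares the texts and then measures the interval.

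**1. One case against each section.** Take a new, suspected-related SAE four months after the last dose, with the study still open.

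| Source | Answer for this event |
|---|---|
| 4.2.2, reporting period | Outside it (limit is 30 days) |
| 4.2.2, late clause, completion as in Section 8 | Not yet in force |
| 4.2.2, late clause, study period as in Section 4.7 | In force from Day 31 |
| 4.2.3 and 7.1 | Report; no end date given |
| 4.2.4 and 7.2 | Inform the IRB or IEC; the study is still running |

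If 4.2.3 and 7.1 are read as procedures that operate inside the 4.2.2 period, they no longer conflict with it, but they are then silent on the interval. If completion is read per subject as Section 4.7 suggests, the gap closes, but only against the definition in Section 8. No reading makes all the sections agree.

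**2. Active collection.** Table 3.6-3 has no AE/SAE mark after the 30-day visit. The 3-monthly list in Section 3.6 contains disease evaluation (only for subjects who stopped without progression or new therapy), one antibody sample at 3 months, survival status and later therapy. None of these asks about an SAE, a cause of death or its relationship to the drug.

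**3. Length of the interval for the last subject entered.** Inputs are the study end at 365 days after the last entry (Section 3.8) and the close of reporting at 30 days after the last dose (Section 4.2.2). It is assumed that completion under Section 8 falls at the Section 3.8 study end.

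Interval = 365 − (days from first to last dose) − 30; months = days / 30.44.

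| Treatment received | First to last dose (days) | Interval (days) | Months |
|---|---|---|---|
| One every-3-week dose | 0 | 365 − 0 − 30 = 335 | 11.0 |
| Weekly, Cycle 1 only (last dose Study Day 15) | 14 | 365 − 14 − 30 = 321 | 10.5 |
| Two cycles, every 3 weeks | 21 | 365 − 21 − 30 = 314 | 10.3 |
| Two cycles, weekly | 35 | 365 − 35 − 30 = 300 | 9.9 |
| Six months of treatment | 183 | 365 − 183 − 30 = 152 | 5.0 |

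A subject entered *d* days earlier with the same treatment duration has an interval *d* days longer.

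**4. Contacts already inside the interval.** Contacts at 3, 6 and 9 months after the last dose fall at about 91, 183 and 274 days. In the one- and two-cycle cases the study ends 330 to 365 days after the last dose, so all three lie between Day 30 and study end.

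**5. Overlap with dosing of others.** Take a Cohort 6 subject entered on day *x* who stops after one dose, with no DLT in Cohorts 6 or 7.

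- Reporting for this subject closes at *x* + 30.
- Cohort 6 cannot finish before *x* + 21 (Section 4.9 item 3).
- Cohort 7 needs at least 7 days for its first subject and then 21 days for the next two: 7 + 21 = 28 (Section 4.9 items 2 and 3).
- The every-3-week expansion waits for both cohorts (Section 2.4), so it cannot open before *x* + 21 + 28 = *x* + 49.

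The subject has left the reporting period at least 49 − 30 = 19 days before that expansion can start, whatever the accrual rate.

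**The case against.** The strongest reply is that reporting is already covered. Section 4.2.3 sends every identified SAE to the sponsor within 24 hours, Section 7.1 repeats the duty regardless of causality, and Sections 4.2.4 and 7.2 run with the study. A site obliged to report related events indefinitely after completion would hardly think itself free to withhold them earlier.

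There is other cover too. Section 3.6 tells subjects to call about abnormalities and has the investigator obtain records of visits to outside facilities. All subjects are due an antibody sample at 3 months, and some are examined and scanned every 3 months. A fatal AE is an SAE by definition, and Section 4.2.5 requires a relationship assessment for each SAE. Section 5.4 limits the AE and SAE summaries to 30 days after the last dose, so late events would not enter them in any case. The day counts measure follow-up time, not missed events.

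Much of this stands. The text does not waive reporting, a 30-day window is not in itself an error, the planned summaries would not change, and the number of events at risk of being missed is unknown. But the cover is passive. Outside records are obtained only once the site knows of a visit, and a relationship assessment follows only once a report is filed. The general duties help only if the site reads them as overriding the section that sets the reporting period.

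**Conclusion.** The concern holds and should be fixed. Section 4.2.2 gives no rule for new suspected-related SAEs from Day 31 after the last dose to study completion, other sections point in different directions, and no scheduled contact asks. For a last-entered subject who stops within two cycles the interval is 300 to 335 days, about 10 to 11 months; after six months of treatment it is 152 days.

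These lengths assume that the Section 8 completion date coincides with the study end in Section 3.8. They describe time at risk of non-reporting, not a count of lost events. The consequence is for ongoing safety review and for stopping rule 4.8 item 1. The 3+3 decisions, the MTD and the sample size are untouched, because DLTs are counted in Cycle 1 only.

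**What to change.** In Section 4.2.2, change the opening of the late clause to: *At any time after the 30-day reporting period, including after completion of the study*.

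Add one line to the 3-monthly contact in Table 3.6-3 and to item 3 of the matching list in Section 3.6. It should ask whether any SAE suspected to be related to MEDI-575 has occurred and, for a death, its cause and relationship to the drug.

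The cost is one phrase and one line in a contact that already takes place for all subjects. A few more reports will come in, some of them confounded by progression or later therapy.
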